9.6 Data Analyses

To address the study objectives, we will quantify the within-person percent change in proposed primary biological signature: brain GSH. We will fit a general linear model with brain GSH as dependent variable with group (NAC high vs NAC low vs PBO) as the predictor variable of interest. Since we apply a minimization procedure to ensure that groups are similar on key demographic and baseline clinical variables (age, baseline NSSI severity, presence of concurrent psychotropic medication), as is typically done in a large clinical trial we will not include covariates. Should the primary outcome values be highly skewed, we will use non-parametric tests instead to compare groups. We will use the standardized Wilcoxon test statistic with the Dwass, Steel, Critchlow-Fligner (DSCF) multiple comparison analysis. This analysis takes each pair of groups, one pair at a time (high NAC vs. low NAC; high NAC vs. placebo; low NAC vs. placebo), computes a Wilcoxon test statistic to compare the two groups in that pair, and obtains a pvalue that is analogous to Tukey's control of family-wise Type I error (the test statistic is scaled to Tukey's studentized range distribution) (Hollander and Wolfe, 1999). This analysis to compare the 3 treatment groups on the primary outcome will adjust type I error using Tukey's procedure for the 3 pairwise comparisons among the 3 groups. Tukey's procedure is less conservative than the Bonferroni adjustment used in the sample size/power

calculation, hence we expect slightly higher power than planned. We will quantify the effect size of each group's change to determine next steps with the research.

To assess the robustness of our conclusions about the primary outcome to participants whose medical profile changes during the course of active treatment in our study, we will conduct sensitivity analyses. For example, if participant(s) need to have a change in their non-study medications during our study, they will remain in the study but the changes in medications will be noted in the study database. We will repeat our primary analysis excluding such people to see if our conclusions remain the same. We note, however, that this analysis is not protected from bias by the randomization.

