To address the secondary study objectives of exploring additional potential biosignatures, we will fit similar general linear models with each of the additional outcomes (brain Glu, blood GSH/GSSG, antioxidant protein levels, GABA concentrations, amygdala-insula functional connectivity) as dependent variables, with group (NAC high vs NAC low vs PBO) as the predictor variable of interest, again without including covariates to preserve power. These secondary analyses will use Holm's step-down Bonferroni type I error correction to adjust for both multiple comparisons among groups and multiple testing across the several secondary outcomes.

Data analysis: To address the secondary outcome of NAC PK, NAC and GSH concentration-time data will initially be analyzed by non-compartmental methods. WinNonLin Phoenix (Pharsight®) will be used to calculate the partial NAC area under the curve (AUC_0-2h) using the linear trapezoidal rule and maximum concentration (Cmax). The AUC_0-2h and Cmax for GSH will also be calculated. Descriptive statistics of the PK parameters will be determined. Drug concentrations and other PK variables will be correlated with degree of change in biological signatures.

To address the secondary objective of describing the tolerability of oral NAC at the proposed study doses, we will quantify rates of side effects and other adverse events and compare rates between groups using Poisson, survival, or other rate-based models as appropriate for each event type.

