Cramér-Rao lower bounds, will be identical to those described before (Terpstra et al. 2016). Functional imaging acquisition and analysis (to obtain secondary outcome amygdala-insula RSFC): Functional data will be acquired using the Human Connectome Project multiband echo planar imaging sequence for 7T (Van Essen et al. 2012; T Vu et al. 2017). Whole brain T2*-weighted functional volumes (85 contiguous slices; TR=1000 ms; TE=22.2ms; flip angle=45°, matrix=208x208mm; voxel size=1.6mm isotropic; multiband factor=5, GRAPPA=2, echo spacing = 0.64ms) will be obtained during rest. Patient will be instructed to keep eyes open while viewing a fixation cross (2 runs at 6 min each). The duration and the choice of fixation cross as the resting condition are selected to optimize reliability (Birn et al. 2013; Patriat et al. 2013). Whole-brain functional connectivity maps of the amygdala will be obtained for each person at each time point using methods described previously ([name] et al. 2014; Westlund Schreiner et al. 2017). We will extract the mean z-score from anatomically-defined insula regions of interest, to represent amygdala-insula connectivity at each time point. These values will be used in repeated-measures ANOVAs to evaluate change in amygdala-insula connectivity over time.

Supplement III: Identification of Potential Participants

- 1) For those screened out or enrolled in previous research study, research staff will identify those that may be eligible for this study and contact them. For those enrolled in previous study, we will only contact those that have indicated in previous consent forms an interest to be contacted about future studies.

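### Amygdala-insula connectivity is given two different analyses, and neither states the change scale together with a group comparison

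*Combined protocol and SAP*

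**What the plan says.** Section 9.6 describes the primary analysis first: "we will quantify the within-person percent change in proposed primary biological signature: brain GSH". The next sentence gives the model: "We will fit a general linear model with brain GSH as dependent variable". It does not repeat whether the dependent variable is the percent change, the absolute change or the Visit 4 value.

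For the secondary biosignatures, with amygdala-insula connectivity named among them, 9.6 continues: "we will fit similar general linear models with each of the additional outcomes", "with group (NAC high vs NAC low vs PBO) as the predictor variable of interest, again without including covariates to preserve power". Holm's correction then covers the group comparisons and the several secondary outcomes together. No change scale is given for any of these outcomes.

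Supplement II (Neuroimaging Procedures) defines the measure: "We will extract the mean z-score from anatomically-defined insula regions of interest, to represent amygdala-insula connectivity at each time point". It then gives an analysis: "These values will be used in repeated-measures ANOVAs to evaluate change in amygdala-insula connectivity over time". It names neither a group factor nor a group-by-time term. Neither place refers to the other.

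The hypothesis in section 9.1 is that one or both NAC doses, but not placebo, increase connectivity. It has no percentage threshold, whereas the GSH, glutamate and blood GSH/GSSG hypotheses do. Section 9.5.2 places the measurements at Visits 2 and 4.

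**The concern.** One named secondary outcome has two written analyses that answer different questions. Section 9.6 asks whether the groups differ. Supplement II asks whether connectivity changes over time. A test of time alone cannot address a hypothesis about NAC but not placebo, and it produces none of the pairwise group p-values that Holm's procedure in 9.6 needs. With both texts in force, the analysis could be chosen after the data are seen.

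The scale is also open. An analyst following 9.6 could take the Visit 4 value, the absolute change or, by analogy with GSH, the percent change. GSH is a concentration with a positive baseline, so a percentage makes sense there. A connectivity z-score has no such floor: dividing by a baseline near zero inflates the value, and dividing by a negative baseline reverses its sign.

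**Working it through.** **Figures in the plan.** The documents give no power or sample-size figure for connectivity. Their only one, in section 9.2, is for GSH (2.95% detectable difference), without a standard deviation, so it cannot be reproduced. This point does not depend on it.

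**Step 1: the two texts side by side.**

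| | Section 9.6 | Supplement II |
|---|---|---|
| Model | general linear model | repeated-measures ANOVA |
| Effect named | group (three levels) | time (two visits) |
| Group term | yes | not stated |
| Use of baseline | no covariate; change scale not stated | z-score at each visit |
| Multiplicity | Holm | not stated |

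**Step 2: when they agree.** With two visits, the group-by-time interaction is the group effect on D = z(Visit 4) - z(Visit 2). The two analyses therefore coincide if 9.6 means absolute change and the ANOVA tests group-by-time. In one simulated data set (36 participants, 12 per arm):

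- group-by-time F = 5.115, and one-way ANOVA on D F = 5.115 (p = 0.012);
- Visit 4 values alone: F = 3.952 (p = 0.029);
- percent change: F = 0.350 (p = 0.71), with individual values from -332% to +2472%.

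So the undeclared scale can change the answer. Neither condition for agreement is written.

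**Step 3: percent change on a z-score.** Percent change = 100 × (post - pre) / pre. For the same rise of 0.10:

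| Pre | Post | Percent change |
|---|---|---|
| 0.20 | 0.30 | +50% |
| 0.02 | 0.12 | +500% |
| -0.02 | 0.08 | -500% |
| -0.20 | -0.10 | -50% |

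This is arithmetic and needs no assumption about the trial.

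**Step 4: illustrative power.** Assumptions, none of them from the documents: SD 0.15 at each visit, pre-post correlation 0.5, and a high-dose shift of 1.2 SD = 1.2 × 0.15 = 0.18. There are 12 per arm; the test is high dose against placebo, two-sided, at unadjusted 5%, with pooled error.

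- *Absolute change.* SD of D = 0.15 × √(2 × (1 - 0.5)) = 0.15. Standard error = 0.15 × √(2/12) = 0.0612. Noncentrality = 0.18 / 0.0612 = 2.94. Power on 33 df is about 81%, whatever the baseline mean.
- *Baseline-adjusted.* Residual SD = 0.15 × √(1 - 0.25) = 0.130. Simulated power on 32 df is about 90%.
- *Percent change.* Simulated power is about 4%, 9%, 22% and 64% at baseline means of 0.1, 0.2, 0.3 and 0.6. The estimated effect has the wrong sign in about 40%, 31% and 19% of trials at the first three means, and rarely at 0.6.

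**Step 5: at the plan's multiplicity.** Counting catalase and HO-1 separately gives six outcomes × three pairs = 18 tests. Holm's first step is 0.05/18 = 0.0028. There, absolute change has about 40% power and baseline adjustment about 54-55%.

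**The case against.** The strongest defence is that the texts can be read together. Section 9.6 is the analysis section and makes group the predictor. Section 9.1 says the three groups serve to compare pre-post changes. Supplement II describes imaging procedures and may only be summarising. On that reading the ANOVA is a group-by-time test, identical to a group model on absolute change. This is a sensible reconciliation, but it supplies both a group term and a change scale that are not written.

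A reader might infer that the plan will analyse connectivity as percent change and so lose most of its power. The documents do not support that. Section 9.6 states percent change for brain GSH only, the connectivity hypothesis carries no percentage, and Supplement II works with the z-scores themselves. What stands is conditional: the scale is unstated, and the only one named nearby is unsuitable here.

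The power figures are also open to challenge. Their inputs are assumed, the loss shrinks as the baseline mean rises, and unadjusted 5% is not the plan's criterion. If *similar* imports percent change, it arguably imports the primary outcome's fallback to Wilcoxon tests under high skewness too. That fallback gives 17%, 41% and 57% at means of 0.1, 0.2 and 0.3: still below absolute change, but a smaller loss. These limits stand.

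Finally, a baseline covariate departs from the no-covariate rule in 9.6. The reason given there is power, and under the assumptions above adjustment raises power from about 81% to 90%. An uncovaried alternative would also resolve the conflict.

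**Conclusion.** The point holds as an inconsistency and an omission. The inconsistency is on the page and rests on no assumption: a group model with no stated scale in 9.6, and a time analysis with no stated group term in Supplement II. A reader might conclude that the trial intends a placebo-free test of connectivity. Section 9.6 does not support that; the narrower finding is that the Supplement II analysis, run exactly as written, would not compare NAC with placebo.

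The unsuitability of percent change for a z-score is arithmetic, but whether the plan means to use it is not established. The size of any loss depends on the unknown baseline distribution: about 4% to 64% power for baseline means of 0.1 to 0.6, against about 81% and 90%, under the stated assumptions at unadjusted 5%. These figures are illustrative and do not estimate this trial's power.

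The consequence is confined to one secondary outcome and to the p-values it contributes to the Holm family. The primary analysis and the sample size are unaffected.

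**What to change.** State one analysis, in the same words, in section 9.6 and Supplement II:

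- Outcome: amygdala-insula z-score at Visit 4. Factor: group (three levels). Covariate: z-score at Visit 2. Report the adjusted mean difference in z for each pair of groups with its confidence interval.
- If the no-covariate rule is kept, compare absolute change in z (Visit 4 minus Visit 2) between groups, and note that this equals the group-by-time test.
- Enter the resulting pairwise p-values in the Holm family.
- State that percent change is not used for this outcome.
- Replace the repeated-measures ANOVA sentence in Supplement II with a reference to 9.6 or, under the no-covariate option, add the group-by-time term to it.

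The cost is wording only, because both z-scores are already collected. The covariate option needs a stated exception to the no-covariate rule for this outcome. The change should be made before the blind is broken.

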10. DATA COLLECTION AND QUALITY ASSURANCE

10.1 Data Collection Forms

Information will be collected from participants by Principal Investigator, [name], Co-Investigator [name], Research Coordinator, [name], and University of Minnesota Psychology graduate students under the supervision of Drs. [name] and [name]. All study staff collecting information will be blinded. Information will be recorded directly onto paper copies of measures or directly into REDCap as source data. Measures recorded on paper copies will be transferred to REDCap or secure Box, though source data and

confidential information will be kept in a locked cabinet in a locked room.

10.2 Data Management

Storage and Access: Data will be collected using a combination of paper and electronic measures. Data will be stored and administered electronically in a REDCap database managed by the University of Minnesota Academic Health Centers Information Systems (AHC-IS) (<https://redcap.ahc.umn.edu>) and a HIPAA compliant secure UMN Box folder identifiable by subject ID. Demographic information containing PHI, such as age, date of appointments, race, age, etc., will be entered directly, and stored, via an electronic measure, Demographics Form, into REDCap. Neuroimaging data will be stored on secure servers of the Center for Magnetic Resonance Research (CMRR) and will not contain any PHI, identifiable only by subject ID (participant specific) and procedure number (scan specific).

Access to the REDCap project and the UMN Box folder will be granted by Research Coordinator ([name]) and PI ([name]) as “owners” to study staff access as “editors”. REDCap and secure Box are accessible by UMN staff, faculty and students via UMN username and password managed by AHC-IS. The built-in audit trail in REDCap allows administrators to be able to determine all the activity and all the data viewed or modified by any given user in REDCap.

The following measures will be collected and stored for future analysis: Demographic information including sex, age, race, ethnicity, diagnosis and four factor social status via the Demographic Form on REDCap, WASI-II, Edinburgh, PHQ-9, DTS, CTQ, BSS, side effects checklist, SITBI, ABUSI, BDI-II, DSHQ-M, ISAS-Lifetime, Anti-Depressant Medication form, Ongoing Medication Use and Changes: Initial Visit, Ongoing Medication Use and Changes: Subsequent Visits, and ISAS-SLV.

Release/Sharing: For data releases, request for sharing will be made to the PI, [name] and/or co-investigator, [name] and granted on an individual basis. Participants that complete MRI scans will be offered a copy of a portion of their scan on disc. A written report detailing information gathered at the clinical assessment (MINI-KID or MINI), including psychiatric diagnosis, will be shared with participants provider(s) of choice upon receiving signed release of records from the participant. Additional specific measures gathered will be shared with participants providers upon signed request. General findings after data analysis will be shared with all participants in the form of a mailed letter.

Specimen blood samples will be processed for analysis and then stored at the Center for Orphan Drug Research (CODR). These samples will be stored for at least 5 years to allow for follow-up tests that may be required, such as if new tests become available, or if manuscript reviewers request additional analyses.

10.3 Quality Assurance

10.3.1 Training

Investigator and study staff will operate under the standard operating procedures (SOPs) of the University of Minnesota human research protection program found in

the toolkit library at <https://research.umn.edu/units/irb/toolkit-library/standard-operating-procedures>. All study staff on this study will be delegated particular tasks as indicated by the Delegation of Authority Log kept on site. Study staff will be trained on each updated protocol and recorded on a protocol training log.

All study staff will receive HIPAA training via University of Minnesota and Good Clinical Practice training via the Collaborative Institutional Training Initiative (CITI), as required by the UMN Department of Psychiatry. Study staff consenting candidates will each perform a training program documented and signed-off on-site before they perform said activities.

Training oversight

- 1) Delegation of Authority log will show which personnel are delegated to which study procedures.
- 2) Protocol training log will show all personnel up-to-date on current protocol versions.
- 3) Psychological assessment training will be conducted by [name] and reflected in the DoA and Psychological Assessment Training log.
- 4) IV catheter placement and phlebotomy will be conducted by trained Fairview/M Health staff

10.3.2 Quality Control Committee

Quality Assurance (QA) Reviewer will review monthly report of adherence to the treatment protocol and adherence of participants. QA Reviewer will be lab associate not working directly on this project.

10.3.3 Metrics

Quality assurance of metrics will be as follows:

Spectroscopy measures: To ensure identical voxel positioning in the pre- and post-NAC scans, we will utilize the AutoAlign feature on Siemens by saving subject specific protocols at the baseline. Acquisition methods and evaluation of the CSF contribution to the ACC voxel will be as described in our previous work (Terpstra et al 2016, van de Bank 2015). Methods to assess the reliability of metabolite concentrations based on Cramér-Rao lower bounds will be identical to those described in our previous work (Terpstra et al, 2016).

10.3.4 Protocol Deviations

Protocol deviations will be recorded by study staff in a protocol deviation log, with attached memo if further explanation is needed. Protocol deviation logs will be reviewed every 6 months by a study monitor from the Independent Monitoring Committee. This monitor will also review study documentation to assure the protocol deviation log is up-to-date upon review.

Any unapproved protocol deviations (an accidental or unintentional change to the IRB-approved protocol) that, in the investigator's judgment, potentially caused harm

to subjects or others, indicates that the subjects or others are at an increased risk of harm, or has adversely impacted data integrity, will be reported to the IRB promptly and no later than 2 weeks (10 business days) from the time of the identification of the unplanned or unintentional protocol deviation/violation.

There are many unplanned or unintentional violations/deviations or changes in study status that do not cause harm, place subjects at increased risk of harm, or adversely affect data integrity. The IRB does not require that these minor violations/deviations be reported. Examples of minor violations/deviations that do not need to be reported may include the following:

- Out of window visits
- Study procedures conducted out of timeframe
- Subject failure to initial each page of the ICF (as applicable)
- Subject failure to return subject materials (e.g., diaries, journals, etc.).
- Administrative hold on a study not related to safety issues

Examples of accidental or unintentional protocol violations/deviations that must be submitted to the IRB include:

- Changes necessary to eliminate apparent immediate hazards to the subject
- Failure to document informed consent
- Informed consent obtained after initiation of study procedures
- Enrollment of a subject who did not meet all inclusion/exclusion criteria
- Performing study procedure not approved by the IRB
- Failure to report serious adverse event to the IRB and/or sponsor
- Failure to perform a required lab test that, in the opinion of the investigator, may affect subject safety or data integrity
- Drug/study medication dispensing or dosing error
- Study visit conducted outside of required timeframe that, in the opinion of the investigator, may affect subject safety
- Failure to follow safety monitoring plan
- Missing or unreturned investigational product

10.3.5 Monitoring

Data integrity monitoring will be conducted at outset, every 6 months, and upon study closing by the NCCIH. The monitor will review an on-site regulatory binder as well as participant folders to ensure compliance to the protocol, SOP and other regulatory requirements. The monitor will review consent forms, completion of source documents and case report forms, and appropriate documentation for protocol deviations, personnel changes, staff training, and adverse events, etc. The monitor

will have access to and review all necessary documents at a set appointment time. Monitoring reports will indicate enrollment numbers, select changes since the last monitoring visit and any unresolved queries. The research staff will be expected to resolve all queries, and notify monitor of these resolved queries, within 10 days of receiving the monitoring report.

11. PARTICIPANT RIGHTS AND CONFIDENTIALITY

11.1 Institutional Review Board (IRB) Review

This protocol and all consent documents associated with this study protocol (parent consent, adult consent, assent form) and any subsequent modifications will be reviewed and approved by NCCIH, Advarra IRB and the FDA for oversight of the study. The consent forms will be reviewed and approved separate from this protocol document.

11.2 Informed Consent Forms

The consent process will take place at Visit 1, before the clinical assessment. Participants will receive copies of the consent / assent (if applicable), email authorization and HIPAA forms via email or USPS mail at least 24 hours before this appointment. The initial consent process will take place with research staff in a previously reserved room within the Ambulatory Research Center (ARC) at the University of Minnesota Department of Psychiatry (F212) Fairview Riverside West Building or at the Research in Adolescent Depression Lab at the University of Minnesota Medical School in-person or through video conferencing. During the consent process study staff will review the consent forms highlighting the most salient points such as study title, purpose, procedures, risks, benefits, alternatives, confidentiality, research related injury, voluntariness, and any additional signing/initial blocks such as permission to re-contact in the future and share data outside of this research study. Talk-back method will be used during the consent visit to ensure potential participant and/or their parent/guardian (if applicable) are understanding these points. In addition, an approved version of the UCSD Brief Assessment of Capacity to Consent specific to this study will be used with all participants during the consent process. Potential participants that are not able to complete the UBACC or score less than 2 points on each question will not be consented and enrolled into the study. If a potential participant scores 0 or 1 on any question the information pertinent to that question will be reviewed and discussed with the participant. If the potential participant is then able to answer the question in full and research staff determines the potential participant fully understands the material, they will be scored the 2 points and then consented and enrolled (assuring all answers are scored 2 points). In addition to University and department mandatory consent training for appropriate research staff, all new staff will be trained in consent for this research study including observing the consent process, mock consent and observed for consent process. Throughout the course of the research study, participants will be gauged of their comprehension of scheduled procedures as well as comfort and willingness to complete these procedures by staff at each visit/procedure. Consent will be documented in ink or through electronic signatures by signature of

parent/guardian on Parental Consent Form (if applicable), under 18 participants on Assent Form (if applicable), 18 or over participants on Adult Consent Form (if applicable) and completed UBACC form (all participants). Research staff obtaining consent will sign (ink or through electronic signatures) each of these applicable forms and document the consent process using the ICF Documentation Form.

This study will not enroll non-English speaking participants.

Potential participants will be screened to determine if they meet age requirements (16-24). They will be asked to bring or produce identification in case of video conferencing and checked of their age at the consent process. Potential participants that fail to bring or produce identification with DOB will not be consented and enrolled. Potential participants age 16 or 17 will be consented as children and those age 18-21 will be consented as adults.

For those age 16 or 17, parental permission will be obtained from at least one parent to consent children eligible for the study. Parental permission will be attempted to be obtained from both parents unless one parent is deceased, unknown, incompetent or not reasonably available due to travel or work. Permission will be obtained from someone other than a parent only when that person is a legal guardian of the potential participant. Assent will be obtained and documented from all participants that meet criteria and are willing to consent that are age 16 or 17. Documentation will be obtained by child signing Assent Form, along with research staff personnel obtaining consent.

Research staff will use a study specific version of the UCSD Brief Assessment of Capacity to Consent (UBACC) for all potential participants (16-24) at the consent visit.

Participants will be able to opt into receiving unencrypted email communication and from study staff for reminders about appointments or instructions. The participant will not be required to communicate via email, and they may change their mind about email communication at any point during the study by informing the study team of their decision. Participants will also have the choice to opt into using texting communication in this study. Texting would allow study staff to remind participants about their appointments, completing remote assessments, or to provide other study updates. To consent into using texting communications, participants must sign the Text Authorization Form. The paper copy will be scanned onto Box or an electronic signature will be recorded in case the visit is completed through video conferencing.

